While presbyopia is a progressive, age-related condition that results in declining accommodative ability over a period of approximately 20 years,⁶ most people begin to experience functional presbyopic symptoms (near blur, trouble focusing while reading, etc.) around the ages of 40-45 years.⁶ In spectacle wearers, presbyopia is treated with bifocal spectacle lenses. For contact lens wearers, a multifocal contact lens may be used to treat the declining accommodation.

Considering the high prevalence of accommodative insufficiency we found in uncomfortable contact lens wearers with a mean age of 25 years,⁹ it is possible that natural accommodative decline is contributing to contact lens discomfort among wearers with prolonged use of digital devices. This discomfort, or asthenopia, may be especially prevalent in contact lens wearers who are also near-sighted (myopic). Because of basic optical principles, myopic patients have to exert more accommodation when corrected with contact lenses compared to spectacles.¹⁰ This increased demand may be bearable for a young person with adequate accommodation, but a myopic patient could experience accommodative eyestrain and fatigue when corrected with contact lenses that he or she did not experience with spectacles. This study will determine how multifocal contact lens correction affects symptoms of discomfort and asthenopia in a group of myopic contact lens wearers in the non-presbyopic age range.

III. Procedures

a. Research Design

A prospective, randomized, cross-over clinical trial will be performed.

b. Sample

Uncomfortable myopic soft contact lens wearers that fall in the non-presbyopic age group will be recruited. Table 1 lists the complete inclusion criterion. A total of 68 subjects will be recruited. See the Detailed Study Procedures section for a complete sample size justification.

Personal Characteristics	Dry Eye Status	Binocular Vision Status
30-40 years old	≤ Grade 1 ocular surface staining ¹²	≤ 4 prism diopters eso or exophoria at distance and near (via Modified Thoringon) ¹⁴
Visual acuity of 20/25 or better in each eye with habitual correction	Schirmer score ≥ 7 mm ¹³	Near point of convergence ≤ 6 cm ¹⁴
Myopic OU (-0.75 D or more myopic) Spherical OU (-0.75 D or less astigmatism (with autorefraction)	Tear break-up time (TBUT) ≥ 7 seconds ¹³	No history of strabismus, patching

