Pre-presbyopes with symptoms of contact lens discomfort and asthenopia will be recruited from The Ohio State University College of Optometry Clinics. Interested subjects will be instructed to contact investigators by email. The Contact Lens Dry Eye Questionnaire-8 (CLDEQ-8), a survey validated to reflect change in opinion of contact lenses,¹¹ will be administered over the phone to ensure each subject has significant discomfort symptoms. Each subject must have a score of ≥ 12 points¹⁵ to qualify for the first, baseline examination.

At the baseline examination, inclusion criteria will be confirmed. The presence of concurrent dry eye or a binocular vision disorder (a group of disorders that involved how the eyes move together) will confound study results, so subjects with significant signs of these conditions will be excluded from the study (as defined in Table 1). With the each subject's habitual contact lens correction, heterophoria at distance and near and NPC will be measured to determine binocular vision eligibility. Accommodative function will also be assessed at this time. TBUT, ocular surface staining, and Schirmer testing will be performed to determine dry eye eligibility. Keratograph 5M tear imaging will also be performed at this time. A general anterior segment assessment will be made and assessment of the lid margins and Meibomian glands after habitual lens wear will be recorded. The CISS will be administered at the baseline examination. Subjects who meet all inclusion criteria will be enrolled and randomized (blocked randomization design with a 1:1 allocation ratio) to receive either the single vision Bausch + Lomb ULTRA® or single vision Bausch + Lomb ULTRA® for Presbyopia contact lenses first. All subjects who complete the baseline examination (whether enrolled or not) will receive \$40 cash and a parking pass.

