Subjects will be asked which of the two trial lens pairs they preferred and be asked which lens (single vision or multifocal) they think they had first and second. After all testing and procedures have been completed, subjects will be instructed to return to habitual contact lens wear and informed of what lenses they had during the first and second trial periods. Subjects will receive \$40 cash and a parking pass at the end of the third examination.

Data Analysis and Sample Size Justification

Paired *t* tests will be performed to compare mean CLDEQ-8 scores with habitual single vision lenses, single vision Bausch + Lomb ULTRA® contact lenses, or Bausch + Lomb ULTRA® for Presbyopia contact lenses to one another. Repeated measures ANOVA testing will be performed to determine if contact lens comfort (CLDEQ-8 score) is affected by age or magnitude of myopia when subjects are corrected with their habitual single vision lenses, single vision Bausch + Lomb ULTRA® contact lenses, or ULTRA® for Presbyopia contact lenses. CISS scores throughout the trial will be analyzed in the same way as the CLDEQ-8 scores. To determine if accommodative ability is related to multifocal preference, paired *t* tests will be used to compare contact lens preference (single vision versus multifocal) to initial accommodative function (lag/lead) values.

In order to detect a conservative standardized effect size of 0.6 ($\alpha = 0.05$, $\beta = 0.20$), a sample size of 45 subjects would be necessary. A previous cross-over trial utilizing the CLDEQ-8 reported a 20% loss-to-follow-up rate.¹¹ Anticipating and accounting for a similar rate in our subject enrollment, a sample of 54 subjects would be appropriate. Because the hypotheses of this study have never been tested, we recognize that this initial sample size may seem inadequate after all data is collected. So, our initial 54-subject sample size will be increased by an additional 25% to allow for additional data collection that may be necessary. Therefore, 68 subjects (34 subjects per group) will be sought for IRB approval to account for the possibility of needing more subject data to make reliable study conclusions.

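### Measured baseline accommodation is related only to lens preference, by a test that does not fit, and is never directly tested as a modifier of the multifocal comfort benefit

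*Combined protocol and SAP*

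**What the plan says.** II. Background and Rationale puts the mechanism forward as a possibility: "it is possible that natural accommodative decline is contributing to contact lens discomfort among wearers with prolonged use of digital devices". It gives the aim as a lens effect on symptoms: "This study will determine how multifocal contact lens correction affects symptoms of discomfort and asthenopia".

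Table 1 sets entry by age ("30-40 years old"), myopia, device use, CLDEQ-8 of at least 12, dry-eye limits and binocular vision limits such as "Near point of convergence ≤ 6 cm". It has no limit on lag, lead or amplitude.

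The Accommodative Function paragraph has response measured by autorefractor at 2.00 and 4.00 D with the habitual, single vision and multifocal lenses. At the baseline examination it is measured first in habitual lenses and again in the first dispensed pair.

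The Data Analysis section plans three things:
- Paired t tests of CLDEQ-8 between lenses.
- A model of comfort against two subject factors: "Repeated measures ANOVA testing will be performed to determine if contact lens comfort (CLDEQ-8 score) is affected by age or magnitude of myopia". CISS is to be handled the same way.
- For accommodation, paired t tests to "compare contact lens preference (single vision versus multifocal) to initial accommodative function (lag/lead) values". Preference is asked once, at the final examination, as a choice between the two study pairs.

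**The concern.** There are two problems.

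First, the named test does not match the data. Each subject has one preference and one initial lag value per stimulus level. The comparison is between two separate sets of people, so there is nothing to pair.

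Second, the variable closest to the proposed mechanism never meets the main outcome. Age and myopia stand in for accommodative ability and demand, but the measured response is left out of the CLDEQ-8 and CISS models. Preference is a weak substitute. It keeps only the direction of a difference that the trial records as a score, and it may turn on things other than comfort, such as vision.

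At stake is how the trial will be read. If benefit depends on accommodation, the planned comparison could miss it, or could show a relation with preference that says little about comfort. If the mean lens effect is small, no planned analysis of the symptom scores asks whether subjects with greater lag gained more.

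**Working it through.** **The plan's own figure.** For a standardized effect of 0.6, two-sided alpha 0.05 and power 80%, a two-sample t test needs 44.6, that is 45 per group. This matches the stated 45. (A paired t test with 0.6 on the SD of the differences needs 24.) Then 45 × 1.20 = 54 and 54 × 1.25 = 67.5, rounded to 68. Neither these steps nor the dated updates concern accommodation. The 8/14/2017 increase rests on an age-group interaction (p = 0.12).

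**Number available.** The 11/21/2017 update gives 69 enrolled, 15 of them in the new round: 69 − 15 = 54 before it. Adding the 30 sought gives 84 enrolled. With the plan's 20% loss, 84 × 0.80 = 67.2, or about 67 completers.

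**What the added test is.** With two lens conditions, the lens-by-lag interaction is the slope of the within-subject difference (multifocal minus single vision) on baseline lag. Its power depends on the correlation r between the two. The documents give no r, so 0.30 and 0.40 are assumed, with 0.20 as a pessimistic check.

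**Continuous analysis.** Power ≈ Φ(atanh(r) × √(n − 3) − 1.960). At n = 67, √64 = 8.
- r = 0.30: 0.3095 × 8 − 1.960 = 0.516, power 70%.
- r = 0.40: 0.4236 × 8 − 1.960 = 1.429, power 92%.

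**Preference analysis, best case.** Let preference be exactly the sign of the score difference, split 50:50. Cutting a normal variable at its median multiplies the correlation by √(2/π) = 0.798.
- r = 0.30 becomes 0.239: 0.2441 × 8 − 1.960 = −0.007, power about 50%.
- r = 0.40 becomes 0.319: 0.3308 × 8 − 1.960 = 0.686, power about 75%.

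**Simulation check** (bivariate normal, 40,000 runs, independent-samples t test for preference, two-sided 0.05). Results carry an error of up to about one point.

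| Completers | r | Continuous | Preference 50:50 | Preference 70:30 |
|---|---|---|---|---|
| 67 | 0.20 | 37% | 25% | 23% |
| 67 | 0.30 | 70% | 51% | 46% |
| 67 | 0.40 | 93% | 77% | 72% |
| 84 (no loss) | 0.30 | 80% | 60% | 55% |
| 84 (no loss) | 0.40 | 97% | 86% | 82% |

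**Limit of the added test.** For 80% power, n = ((1.960 + 0.842)/atanh(r))² + 3. This gives 194, 85 and 47 for r = 0.20, 0.30 and 0.40. At n = 67 the smallest correlation detectable with 80% power is tanh(2.802/8) = 0.34.

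**The case against.** The strongest reply is that the plan does approach the question. The background describes an age-related decline and an added accommodative demand in myopes who wear contact lenses. Age and magnitude of myopia are the two factors modelled against comfort, and the age-group interaction has already driven a sample-size increase. This stands. A reader might infer that the trial never asks whether benefit depends on accommodation, but it does ask, indirectly. What is missing is the direct test.

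A reader might also infer that entry is at fault for not selecting poor accommodators. The documents do not support that. The objective is the effect of multifocals on comfort in non-presbyopic wearers, and broad entry suits it. Myopia, at least 3 hours of daily device use and age 30 to 40 already lean towards the hypothesis. The recruitment sentence ("Pre-presbyopes with symptoms of contact lens discomfort and asthenopia will be recruited") is not contradicted by the lack of a CISS threshold, because the background uses discomfort and asthenopia together and describes CISS as a convergence insufficiency survey.

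Two more replies have weight. Preference might reflect ease of near vision, and so track accommodation more closely than a dry-eye score does. The power loss shown is therefore conditional on preference standing in for comfort. The fitting rule that accepts binocular vision better than 20/40 also requires comfort and proper fit, so it does not show that vision decides preference. Finally, the added test is itself short of 80% power at r = 0.30 with 67 completers, so a null result would not rule out a modest relation.

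**Conclusion.** The point holds in a limited form. The documents establish that measured accommodation enters one analysis only, that the test named for it cannot be applied to two different sets of people, and that no planned model relates it directly to CLDEQ-8 or CISS.

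At about 67 completers and r of 0.30 to 0.40, moving from preference to the score raises power by roughly 16 to 19 points (77 to 93%, 51 to 70%). This rests on the assumed r, normality, a 50:50 split, preference that mirrors comfort, and 20% loss.

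Two stronger readings are not supported. The background says accommodative decline is possibly contributing to discomfort, not that it causes it. Nor can one say how far the mean lens effect is diluted by subjects with good accommodation: the documents give neither the share of this sample with a deficit nor their expected gain.

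**What to change.** 1. In the CLDEQ-8 and CISS models comparing multifocal with single-vision ULTRA, add baseline lag/lead as a continuous covariate with its lens-by-lag interaction.
2. Use the measurement taken in habitual lenses at the baseline examination, before any study lens is dispensed. The one taken in the first dispensed pair depends on sequence. Fix one stimulus level, 2.00 or 4.00 D, now.
3. Label the interaction a secondary test of the accommodative hypothesis, because the 8/14/2017 update shows that outcome data have been examined. Report the slope with its confidence interval, so that a null result can be read for what it excludes.
4. Keep preference as descriptive. Compare lag between preference groups with an independent-samples test, or by logistic regression of preference on lag.

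The cost is analysis wording and one additional secondary interaction test per score. The measurements are already scheduled at baseline, and the entry criteria need no change.

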Updated sample size (03/07/2017): At this point in the study, we have seen 26 total subjects: 17 were successfully enrolled and 9 failed to qualify for the study (did not meet all dry eye and binocular vision inclusion criteria) after completing the baseline examination. Therefore, approximately 35% of the subjects who have participated in baseline examinations have failed. With 17 subjects enrolled, we need to recruit and enroll an additional 51 subjects to complete the study. Considering our recent experience with enrollment, we will assume that 35% of these 51 baseline examinations (or about 18) will not qualify for the study. Therefore, we are requesting to increase our original sample size of 68 subjects by 18 and recruit a sample size of 86 (43 subjects per group).

Updated sample size (8/14/2017): Upon initial data analysis of the subjects who have completed the study, we found an interaction between subject age group and change in CLDEQ-8 survey score that, while not statistically significant ($p = 0.12$), was clinically significant (an approximate 4-point difference between age groups) according to CLDEQ-8 interpretation. We have hypothesized that this clinically relevant finding may have lacked statistical significance because of an inadequate sample size. Because of the lack of software or well-developed methods for calculating the sample size for an interaction in a cross-over study, a simulation study was conducted to estimate what a sufficient sample size would be. The simulation assessed adding more subjects to the sample – using

the subjects currently in the sample. This iterative process was conducted to draw 10 different samples from which sample size was estimated in order to attempt to replicate the original finding with greater power. Given the simulation, it was recommended that 30 additional subjects be tested. At this point, approximately 27% of subjects who present for the baseline examination fail to qualify for the study, so we will increase the 30 additional subjects by 27% (8 subjects) and, therefore, increase our overall sample size by 38 subjects. In conclusion, the new number of recruited participants will increased from 86 to 124.

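### The 20% loss allowance multiplies where it should divide (54 enrolled leaves about 43 completers, not 45), and the March 2017 figure of 43 per group counts people who are never randomised

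*Combined protocol and SAP*

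**What the plan says.** The sample size is built up in Data Analysis and Sample Size Justification (section III, Detailed Study Procedures).

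- For the chosen effect size, "a sample size of 45 subjects would be necessary".
- A previous crossover trial with the same questionnaire "reported a 20% loss-to-follow-up rate". Allowing for a similar rate, "a sample of 54 subjects would be appropriate".
- Because the hypotheses are new and more data might be wanted, "our initial 54-subject sample size will be increased by an additional 25" percent. As a result, "68 subjects (34 subjects per group) will be sought for IRB approval".

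The update dated 03/07/2017 reports 26 people examined, of whom 17 were enrolled and 9 failed to qualify. It says 51 more must be enrolled, takes 35% of 51 (about 18) as expected failures, adds these to 68, and asks to "recruit a sample size of 86 (43 subjects per group").

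The update dated 8/14/2017 gives a failure rate of about 27% and raises the recruited total to 124, in order to test 30 more subjects. The update dated 11/21/2017 raises it to 144 and reports 69 enrolled and 35 failed, with 15 of each in the new round. Neither gives a per-group number.

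Under Subject Enrollment and Baseline Examination and Fitting, only people whose eligibility is confirmed at the baseline examination are enrolled and randomised, 1:1.

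**The concern.** Two stated figures do not follow from the plan's own inputs.

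First, a loss rate is a fraction of those who start. Adding 20% of the target to the target does not restore the target once 20% of the enlarged number is lost. On its own inputs, the number offered as allowing for loss falls short of the number called necessary.

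Second, the term per group changes meaning between two adjacent paragraphs. The 34 per group divides the 68 that the March update goes on to treat as enrolled. The 43 per group divides a count that includes people expected to fail screening, who belong to no sequence.

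What is at stake is how the size is reported. A reader would take 43 as the number randomised to each lens order, and 54 as sufficient for 45 completers. The 43 is also the last per-group figure in the document, so nothing later corrects it.

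**Working it through.** **Inputs.** From the main sample size paragraph: 45 needed, 20% loss, 54, a further 25%, 68. From the 03/07/2017 update: 26 seen, 17 enrolled, 9 failed, 51 still to enrol, 35% failure. From the 8/14/2017 update: 27% failure, 30 additional subjects. From the 11/21/2017 update: 69 enrolled and 35 failed, with 15 and 15 of these in the new round.

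**Reproducing the plan's figures**

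- 45 × (1 + 0.20) = 54
- 54 × 1.25 = 67.5, rounded to 68; 68/2 = 34
- 9/26 = 34.6%, about 35%; 0.35 × 51 = 17.85, about 18
- 68 + 18 = 86; 86/2 = 43

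Every step reproduces, so the method behind each figure is clear.

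**Loss allowance**

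- Completers = enrolled × (1 − loss), so enrolled = completers/(1 − loss).
- 45/(1 − 0.20) = 56.25, so 57.
- Check: 54 × 0.80 = 43.2, about 43; 57 × 0.80 = 45.6, which covers 45.
- The largest loss at which 54 still leaves 45 is 9/54 = 16.7%, below the 20% cited.

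**Whether the shortfall persists**

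- At the 68 sought for approval: 68 × 0.80 = 54.4, about 54 completers.
- At the 69 enrolled by 11/21/2017: 69 × 0.80 = 55.2, about 55 completers.
- Both exceed 45.

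**Per-group figure**

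- 86 = (17 + 51) to be enrolled + 18 expected failures.
- Intended randomised number: 86 − 18 = 68, or 34 per sequence. The stated 43 is 43/34 = 1.26 times that.

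**What 86 examinations would yield**

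- At 35% failure: 86 × 0.65 = 55.9, about 56 randomised, 28 per sequence. Counting forward from the 17 already enrolled gives the same: 17 + 0.65 × (86 − 26) = 56.
- At 27% failure: 86 × 0.73 = 62.8, about 63 randomised, 31 per sequence.
- The 27% agrees with the later counts. Before the new round there were 69 − 15 = 54 enrolled and 35 − 15 = 20 failed, and 20/(54 + 20) = 27%.
- There are two reasons why 86 falls short of 68 enrolled. The update adds 35% of 51 where it should divide (51/0.65 = 78.5, so 79 examinations, not 69), and it leaves out the 9 who had already failed.

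**Current enrolled target, reconstructed**

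- Enrolled before the new round: 69 − 15 = 54. This is an observed count, and it equals the planned 54 only by coincidence.
- 54 + 30 = 84, or 42 per sequence.
- At the cited 20% loss: 84 × 0.80 = 67.2, about 67 completers.

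**The case against.** The strongest reply is that the first error never reached the operative design. The same paragraph raises 54 to 68 before approval is sought, and 54 survives afterwards only as a recruitment forecast under Timeline. This stands, and it is why the point is minor. It does not make the 54 correct: the 25% was justified as room for further data, not as a loss allowance.

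A second reply is that the 43 belongs to a dated entry that the totals of 124 and 144 have overtaken, that the entry speaks of recruiting, and that it says just beforehand that about 18 will not qualify. A careful reader could work out the meaning. However, the dated entries form part of the current sample size section, the Figure 1 caption sends readers there for the updated numbers, and no later per-group figure replaces the 43.

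Third, the 35% rate rested on 26 people and was later reported as 27%. That is right, so the yield of 28 per sequence should be read together with 31. Neither reaches 34.

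A reader might go further and infer that the trial is underpowered, or attach a power loss to 43 against 45. The documents do not support that. They do not define which standard deviation the effect size of 0.6 refers to, so no particular power figure can be attributed to the plan. In any case, 43 completers is not what 68 or 69 enrolled would give at 20% loss. Nor should the two 43s be linked: one is total completers from 54 enrolled, the other is half of 86 examinations.

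**Conclusion.** The point holds as a correction to stated figures, with little practical consequence.

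- The allowance for 20% loss should give 57, not 54. As written, 54 enrolled yields about 43 completers, two short of 45. The 68 sought and the 69 enrolled both cover the 45.
- The 43 per group is a count of baseline examinations. The intended randomised number is 34 per sequence, and 86 examinations would have produced about 28 to 31.

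The completer figures assume that the 20% from the cited trial applies here. The plan does not report this trial's own completion rate, although the 8/14/2017 update shows that some subjects had completed by then. The 84 is a reconstruction that counts the 30 additional subjects from the start of the new round, as the 11/21/2017 update does. The plan states no enrolled total, so the sponsor should confirm it. The resulting 42 per sequence is close to 43 only by chance, since it includes the 30 added in August 2017. Whether 144 examinations are enough to reach 84 is not examined here.

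**What to change.** In Data Analysis and Sample Size Justification and its dated updates:

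1. State that 54 enrolled is expected to give about 43 completers at 20% loss and that 57 would give 45. Note that the increase to 68 covers the difference.
2. Replace the 43 per group with the randomised number per sequence (34 intended).
3. Label 86, 124 and 144 as numbers of baseline examinations.
4. State the current enrolled target: the 54 enrolled before the new round (69 − 15) plus 30, which is 84, or 42 per sequence. Give expected completers as about 67 if the cited 20% applies, and replace that rate with the trial's own completion rate.

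The cost is a few corrected figures and labels, which make the stated numbers slightly less favourable. No extra subjects and no change to design or analysis are needed.

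### The 8/14/2017 increase of 30 subjects was prompted by an age-group interaction at p = 0.12 with no extension rule or alpha control, so that interaction should be labelled exploratory

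*Combined protocol and SAP*

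**What the plan says.** Under Data Analysis and Sample Size Justification, the plan compares CLDEQ-8 between lenses with paired t tests. It then uses repeated measures ANOVA to ask whether age or degree of myopia affects the score over three lens conditions (habitual, single vision, multifocal). No age groups are defined. The sample size rests on a standardized effect of 0.6 with alpha 0.05 and beta 0.20: 45, raised to 54 for loss to follow-up, and then by a further 25% to 68 in case more data are needed. No trigger or error adjustment is attached to that 25%. The update of 03/07/2017 treats 68 as the enrolment target: "With 17 subjects enrolled, we need to recruit and enroll an additional 51 subjects to complete the study".

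The update of 8/14/2017 reports an outcome analysis made during the trial: "Upon initial data analysis of the subjects who have completed the study, we found an interaction between subject age group and change in CLDEQ-8". The p-value was 0.12 and the difference between age groups about 4 points. The update continues: "We have hypothesized that this clinically relevant finding may have lacked statistical significance because of an inadequate sample size". On the enlargement it says that "a simulation study was conducted to estimate what a sufficient sample size would be". Subjects were added to the existing sample by drawing on those already in it: "This iterative process was conducted to draw 10 different samples from which sample size was estimated". The result: "Given the simulation, it was recommended that 30 additional subjects be tested". The stated aim is only to repeat the finding with more power than before; no power value is given.

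The update of 11/21/2017 shows the extension still under way: 69 enrolled and 35 baseline failures in total, of which 15 and 15 belong to the new round.

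**The concern.** The data that suggested the interaction also decided that more subjects would be enrolled, and those data remain in the final sample. When a trial is extended because a result is promising but not significant, and the pooled data are then tested at 0.05 as if the size had been fixed, the error rate depends on two things. One is the rule for extending; the other is what would have happened otherwise. Neither is written down. Nor is it stated whether the interaction is exploratory or confirmatory, how many subjects were analysed, which test was used, or whether the age grouping was set before the look.

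A simulation that redraws from subjects already seen builds in the observed effect. The 30 is therefore conditional on that effect being true, and the reader is not told with what power.

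At stake is how the age result is read. A pooled p < 0.05 could be taken as confirmation at a 5% level that has not been established. A pooled p > 0.05 could be taken as evidence of no age effect, although the extension may have had only moderate power for the effect that prompted it.

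**Working it through.** **The plan's own figures.** Enrolled at the look: 69 - 15 = 54. Failures: 35 - 15 = 20. 20/74 = 27.0%, which agrees with the 8/14/2017 statement that "approximately 27% of subjects who present for the baseline examination fail to qualify for the study". 30 x 0.27 = 8; 30 + 8 = 38; 86 + 38 = 124. The 30 itself cannot be reproduced, because the power target, SD, number analysed and simulation model are not given.

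**Number analysed (assumed).** Completers are at most 54. A 20% loss (the rate the plan uses) gives 43. Enrolment from 17 to 54 in 160 days is 1.6 per week, so 6.5 to 9.7 subjects would be in progress for 28 to 42 days of follow-up if the pace was even. Taking 10 gives 54 - 10 = 44, or 0.8 x 44 = 35 after loss. The range used is 35 to 54.

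**Precision at the look, 1 df.** Two-sided p = 0.12 gives z = 1.555. SE = 4/1.555 = 2.57; 95% CI 4 ± 1.96 x 2.57 = -1.0 to 9.0 points.

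**Power of the pooled test at two-sided 0.05, true effect equal to the observed one.**
- 1 df (two age groups, change score): power = Phi(1.555 x sqrt(N/n1) - 1.96), where n1 is the number at the look and N the final number.
- 2 df (two age groups, three lens conditions): the observed chi-square is 4.241, noncentrality 4.241 x N/n1, critical value 5.991.

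| n1 to N | Basis | 1 df | 2 df |
|---|---|---|---|
| 54 to 78 | 24 of 30 complete | 46.4% | 59.3% |
| 54 to 84 | all 30 complete | 49.2% | 62.8% |
| 43 to 67 | 24 of 30 complete | 49.2% | 62.9% |
| 43 to 73 | all 30 complete | 52.6% | 66.9% |
| 44 to 84 | 10 in progress join | 57.5% | 72.3% |
| 35 to 67 | as above, 20% loss | 57.6% | 72.4% |
| 35 to 75 | 35 plus 40, no further loss | 62.4% | 77.5% |

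With t and F reference distributions the last row is 63.5% and 78.0%. Outside this range, 30 to 84 gives 74% and 88%. Three age groups on 4 df give 74% (54 to 78) to 87% (35 to 67). The figures on more than 1 df are optimistic, because an observed chi-square tends to overstate the true noncentrality.

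**Type I error, 1 df.** Under no interaction, the look statistic Z1 and the pooled statistic Z2 have correlation sqrt(n1/N). The extension rule is unknown, so it is varied: extend if 0.05 <= p < 0.12, 0.15, 0.20, 0.30, or whenever not significant.

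- Significance could be claimed at the look: error = P(|Z1| > 1.96) + P(extend and |Z2| > 1.96).
  - 54 to 84: 6.2, 6.5, 6.9, 7.3, 7.8%.
  - 44 to 84: 6.1, 6.4, 6.8, 7.3, 8.2%.
- No claim at the look, and 68 enrolled unless extended to 84: error = P(extend and |Z2| > 1.96) + P(not extended and the statistic at 68 exceeds 1.96 in size).
  - 54, 68, 84: 4.9, 5.0, 5.1, 5.3, 5.7%.
  - 44, 68, 84: 4.9, 4.9, 4.9, 5.0, 5.5%.

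Applying 20% loss to all three counts leaves the ranges at about 6-8% and 4.9-5.7%.

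**The case against.** The update is open about the look, the p-value, the motive and the method, and it speaks of a hypothesis, not of a proven effect. Age was already a planned factor. The study objective and the paired t tests concern lenses, and the interaction is secondary to them. All of that stands. It does not supply an error rate, a definition of the groups or a status for the interaction.

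A reader might infer that the extension raised the false-positive rate to 8%. The documents do not support that. The 6-8% range needs a significance claim to have been possible at the look, and no section provides for one. The 03/07/2017 update suggests that 68 would have been enrolled anyway, and only 54 had been by 8/14/2017; on that reading the excess is negligible. Against this, the sample size section calls 54 the initial sample and treats the rest as an allowance. The question stays open.

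A reader might also infer that the 30 is an error because it falls short of 80% power. That is not supported either. The 80% belongs to the standardized effect of 0.6 and is not tied to the interaction. The 8/14/2017 update aims only at more power than before, and on 1 df power does rise from 34% at the look. The number analysed, the df and the final size are unstated, and some combinations exceed 80%. The power figures serve as a caution on reading the result, not as a shortfall against the plan.

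**Conclusion.** The point holds as a matter of status and reporting. The age-group interaction prompted the enlargement, the same data stay in the pooled test, and no extension rule or alpha control exists. A pooled p < 0.05 is therefore not shown to carry 5% error. The excess may be a few points or close to nothing, depending on a continuation rule that the documents leave open.

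The 30 takes the observed effect as true and comes without a power. For 35 to 54 completers at the look, the power under that same assumption is moderate, so a non-significant pooled result should not be read as no age effect. These figures assume two-sided testing at 0.05, two age groups, and completer counts that the plan does not give.

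Nothing here shows that the main lens comparisons are affected: the update names only the interaction as its reason. This is a cheap improvement. Confidence is moderate, because the sizes rest on unstated counts and an unstated test.

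**What to change.** Add to the SAP: *The age-by-lens interaction is exploratory, because the 8/14/2017 sample-size increase was based on it.* Then:

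- Report the interaction as an estimate with 95% CI. Make no confirmatory claim from a pooled p < 0.05, and no claim of no effect from p > 0.05.
- Show subjects included in the 8/14/2017 analysis separately from those not included, as description only. Subjects in progress on that date fall in the second set.
- State the number analysed on 8/14/2017, the test and its df, the age grouping, and whether the grouping was set before the look.
- If the 30 is still called sufficient, give the power computed from the actual count and test, and say that it takes the observed effect as true. Do not print an assumed range such as the one above; the study team holds the real inputs.

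The cost is a few sentences and one descriptive table, with no new subjects. The downside is a weaker claim for the interaction.
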